- *Annual change in BMD (L1-L4) Z-score:* In the Bone Mineral Density in Childhood Study (BMDCS), mean annual change in BMD (L1-L4) Z-score in 6- to 15-year-old healthy subjects was, as expected, minimal (0.01-0.07). The standard deviation (SD) varied from 0.3 to 0.48 across sex and age groups. Assuming an SD of 0.4, with 100 completed subjects per group, the 95% CI for the treatment difference will have a precision of 0.12.
- *Annual change in height Z-score in the 2- to 9-year-old age group:* In the monotherapy epilepsy study TOPMAT-EPMN-106, the observed change from baseline in mean height Z-score at 1 year among the 2- to 9-year-old subjects treated with topiramate 400 mg/day was -0.18, with an SD of 0.28. Assuming that 53% of the subjects will be recruited in the 2 to 9-year-old age group, ie, 53 completed subjects per treatment group, the 95% CI for the treatment difference will have a precision of 0.11.
- *Incidence of kidney stone formation:* In the studies TOPMAT-PEP-3001 and TOPMAT-PEP-1002 in infants (1 month to 2 years of age), a 7% incidence of kidney stones was observed during the 1-year topiramate adjunctive treatment period. A sample size of 100 completed subjects per treatment group will provide a 95% CI (Wilson score CI) for the treatment difference with a width of 0.12, assuming that the incidence of kidney stone formation is 7% and near zero in the topiramate group and the levetiracetam group, respectively.

- *Change in weight Z-score in the 2- to 15-year-old age group:* In the monotherapy epilepsy study TOPMAT-EPMN-106, a -0.59 decrease from baseline in weight Z-score, with an SD of 0.43, was observed after 1 year of treatment with topiramate 400 mg/day. Assuming an SD of 0.43, a sample size of 100 completed subjects per treatment group will provide a 95% CI with a precision of 0.12.

Safety Analyses

The key safety endpoints will include:

- Percentage of subjects with kidney stones
- Change from baseline in weight Z-score over time
- The following height analyses will be conducted for prepubertal subjects 2 to 9 years of age, subjects 10 to 15 years of age, and subjects 2 to 15 years of age:
 - ◇ Height at 1 year postbaseline
 - ◇ Height change from baseline over time
 - ◇ Height Z-score at 1 year postbaseline
 - ◇ Change from baseline in height Z-score over time
 - ◇ Height velocity at 1 year postbaseline
 - ◇ Height velocity Z-score at 1 year postbaseline

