Only AED monotherapy will be used for both treatment groups. However, subjects will not be discontinued from the study if 1 or more concomitant AEDs are added after initiating treatment with study drug. Data will be collected prior to the use of the concomitant AED(s) for the primary analysis. Data subsequently collected while on the concomitant AED(s) will be analyzed in a secondary analysis for each safety outcome of interest.

All subjects will enter a 30-day posttreatment phase after completing the open-label treatment phase.

The open-label treatment phase has 2 periods, titration and maintenance.

Titration Period

Randomization will take place on Day 1 (Visit 2). The Day 1 visit will serve as the baseline visit. All procedures on Day 1 (except dispensing of study drug) should be completed before randomization.

Study drug will be titrated as tolerated to the maximum recommended dosage for optimal clinical effect over approximately 6 to 8 weeks, based on titration guidelines according to clinical response (see Section 6, Dosage and Administration). For all subjects, at any time, up-titration of open-label study drug may be slowed down if clinically indicated for tolerability, and may be accelerated if clinically indicated for seizure control.

Subjects will return for a clinic visit at Month 1 and Month 2 for dispensing of study medication.

Maintenance Period

Subjects should be maintained on the dosage achieved at the end of the titration period through the remainder of the open-label treatment phase, with the option for dosage adjustment as required for optimal clinical effect. Changes to this schedule will be based on a risk-benefit assessment of the subject's clinical condition by the investigator.

Clinic visits will be scheduled at Months 1, 2, 3, 6, 9, and 12/early withdrawal. Extra visits may be scheduled at the discretion of the investigator. Blood samples for PK evaluations will be taken at Months 1, 3, 6, and 12/early withdrawal.

Posttreatment Phase

[figure not shown]
Subjects will be contacted by telephone 30 days after the last dose of study drug to monitor adverse events and concomitant medications. Subjects who complete the study or discontinue early from the study may, at the discretion of the investigator, either continue on commercially available topiramate or levetiracetam or taper off topiramate or levetiracetam over a period of up to 2 weeks during the posttreatment phase.

Post-Study Follow-up Phase

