There may be an optional post-study follow-up phase to obtain DEXA measurements in a subgroup of subjects who experience a clinically important reduction (change in Z-score of -0.5 or greater) in BMD, based on local DEXA scan results, after 1 year of treatment with topiramate, to determine whether a decrease in BMD after or during 1 year of treatment with topiramate is reversible. These subjects will have a repeat DEXA scan 6 months after discontinuation of study drug. During study conduct, the sponsor will assess site/investigator interest for participation in this phase to determine if the follow-up phase will be included. An additional consent/assent will be required for this phase.

An external, independent Data Monitoring Committee (DMC) will be commissioned for this study. See Section 11.5, Data Monitoring Committee, for details.

A diagram of the study design is provided in [Figure 1](#).

Figure 1: Study Diagram

^a Optional post-study follow-up phase to obtain DEXA measurements in a subgroup of subjects who experience a clinically important reduction (change in Z-score of -0.5 or greater) in BMD, based on local DEXA scan results, after 1 year of treatment with topiramate; these subjects will have a repeat DEXA scan 6 months after discontinuation of study drug.

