meals. Study staff will instruct subjects and/or parents/caregivers on how to store medication for at-home use as indicated for this study. If a subject vomits within 30 minutes of receiving a dose, the dose will be repeated. If a subject vomits a second time or more than 1 hour later, the dose will not be repeated. All cases of vomited doses and action taken must be recorded in the subject's take-home record. Subjects will be instructed to take any missed doses of study drug as soon as possible. However, if the subject is within 6 hours of taking the next scheduled dose, he or she should wait until then to take the usual dose of study drug and skip the missed dose. Subjects should not take a double dose in case of a missed dose.

Subjects should be titrated and maintained according to clinical response, eg, titration may be slowed on the basis of tolerability and may be accelerated for the purposes of seizure control. Maintenance dosages should be based on optimal clinical response and may be adjusted at any time during the open-label treatment phase. Subjects are recommended not to exceed maximum recommended maintenance dosages; however, subjects will not be discontinued from the study if higher doses are required for optimal clinical effect as judged by the investigator. Data collected while on dosages that exceed maximal recommendations may be analyzed separately, as appropriate.

Once a subject completes the study or discontinues early from the study, at the discretion of the investigator, he or she will either continue on commercially available topiramate or levetiracetam or be tapered off of topiramate or levetiracetam over a period of up to 2 weeks.

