8. PRESTUDY AND CONCOMITANT THERAPY

Prestudy AEDs and other medications taken within 2 years prior to the study must be recorded at screening.

Concomitant therapies must be recorded throughout the study beginning with the start of the first dose of study drug. Concomitant therapies should also be recorded beyond 30 days after the last dose of study drug, but only in conjunction with new or worsening adverse events or serious adverse events that meet the criteria outlined in Section [12.3.2](#), Serious Adverse Events.

All therapies (prescription or over-the-counter medications, including vaccines, vitamins, herbal supplements; non-pharmacologic therapies such as electrical stimulation, acupuncture, special diets, exercise regimens) different from the study drug must be recorded in the CRF. Modification of an effective preexisting therapy should not be made for the explicit purpose of entering a subject into the study.

For subjects receiving an AED at baseline, this AED should be tapered down and discontinued during the titration period. Concomitant AEDs at baseline used for any purpose will be withdrawn in one-third decrements during the 6- to 8-week titration period.

Only AED monotherapy will be used for both treatment groups. In the event of insufficient seizure control or intolerability, it should be explored first if a dosage adjustment of the study drug might be useful before adding another AED. However, subjects will not be discontinued from the study if 1 or more concomitant AEDs are added after initiating treatment with study drug. Data will be collected prior to the use of the concomitant AED(s) for the primary analysis. Data subsequently collected while on the concomitant AED(s) will be analyzed in a secondary analysis for each safety outcome of interest.

Other prohibited concomitant medications include:

- Ocular medications, except lubricating eye drops or topical antibiotics
- Furosemide, hydrochlorothiazide, vigabatrin, vitamin B₆ therapy for epilepsy, monoamine oxidase (A or B) inhibitors, or felbamate
- Any other medication that is a potent carbonic anhydrase inhibitor (eg, acetazolamide, furosemide, zonisamide)
- Citrate treatment
- Medications that may affect bone metabolism taken for more than a 10-day treatment course, including intravenous or oral steroids, growth hormone, NSAIDs, antacids, calcium, vitamin D, or multivitamins

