7.4. Bone Mineral Density (BMD) and Bone Mineral Content (BMC)

DEXA measurements will include posterior-anterior spine and total body less head areal (TBLH) BMD and BMC. Observed BMD (spine and TBLH) and BMC (spine and TBLH) values change from baseline, Z-scores as well as height adjusted Z-scores for BMD and BMC, change from baseline in Z-scores and height adjusted Z-scores for BMD and BMC, and percent change from baseline in BMD and BMC will be summarized by visit using descriptive statistics. The number and percentage of subjects with a BMD Z-score and adjusted Z-score decrease of >0.5 , >1.0 , and >2.0 will be listed and summarized by visit using descriptive statistics. MMRM analysis will also be performed for changes from baseline, changes in Z-Scores from baseline, and changes in height adjusted Z-Scores from baseline.

Subjects with a clinically important reduction in BMD defined as change in Z-score and height adjusted Z-score of -0.5 or greater) at 6 months or 12 months, will have a repeat DEXA scan 6 months after discontinuation of study drug. These subjects will be summarized and listed in the DEXA table and listing.

The change in BMD z-scores will also be summarized by subject's serum bicarbonate categories.

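### The repeat DEXA meant to test reversibility is timed from stopping study drug, not topiramate, and its summary can mix children on and off topiramate

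*Protocol*

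**What the plan says.** Protocol 3.1 gives the aim of the optional post-study phase: "to determine whether a decrease in BMD after or during 1 year of treatment with topiramate is reversible". Entry is for "subjects who experience a clinically important reduction (change in Z-score of -0.5 or greater) in BMD, based on local DEXA scan results", after a year on topiramate. The timing rule is "These subjects will have a repeat DEXA scan 6 months after discontinuation of study drug", and Protocol 9.1.1, 9.1.5 and the Time and Events footnote use the same clock.

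Protocol 3.1 also says that children who finish or leave early may, at the investigator's discretion, "either continue on commercially available topiramate or levetiracetam or taper off topiramate or levetiracetam over a period of up to 2 weeks". Sections 6, 9.1.1 and 9.1.4 repeat this. No section limits the follow-up phase to children who have stopped topiramate.

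The Month 13 telephone call collects concomitant medication. After that, Protocol 8 has therapies "recorded beyond 30 days after the last dose of study drug, but only in conjunction with new or worsening adverse events" or qualifying serious events.

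SAP 7.4 keeps the study-drug clock but describes the trigger differently: "defined as change in Z-score and height adjusted Z-score of -0.5 or greater) at 6 months or 12 months". It names no arm, and it plans one summary and one listing for these children.

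**The concern.** Reversibility means what happens to bone once the drug has gone. The clock instead runs from the end of the trial supply. The protocol treats the two as different things: the tapering text names the drugs themselves so that commercial product can be used, while the scan clock still refers to study drug.

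If some rescanned children are still taking topiramate, a pooled mean understates any recovery in those who stopped. Separately, children are chosen because their observed change was extreme. Part of an extreme change is usually transient and moves back on the next measurement whatever the treatment. One effect hides recovery and the other imitates it, and a single pooled summary shows neither. No other part of the plan addresses reversibility.

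**Working it through.** **1. Exposure at the repeat scan.** Take a child who ends study drug at Month 12 and moves to commercial topiramate. The repeat scan falls at 12 + 6 = 18 months, after 18 unbroken months of topiramate. The plan is followed exactly, and the scan is six months after study drug.

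**2. What is recorded.** A taper lasts at most 2 weeks, so it ends before the call 30 days after the last dose. The call should therefore show who had stopped and who had continued. From Month 13 to about Month 18 (18 − 13 = 5 months) there is no routine record. A child who stops at Month 15, or restarts, is seen only if an adverse event prompts an entry.

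**3. Dilution.** Let q be the share still on topiramate, R the mean change in children off it and C the mean change in children on it. The pooled mean is (1 − q)R + qC. With C = 0 (an assumption), it is 0.75R at q = 0.25, 0.50R at q = 0.50 and 0.25R at q = 0.75. The documents do not give q.

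**4. Planning inputs (Protocol 11.2).** Dropout 29%; mean annual BMD Z-score change in healthy 6- to 15-year-olds 0.01 to 0.07; SD 0.3 to 0.48; "Assuming an SD of 0.4, with 100 completed subjects per group".
- Sample size: 100/(1 − 0.29) = 140.8, rounded up to 141 per group; 2 × 141 = 282, as stated.
- BMD half-width: 1.96 × 0.4 × √(2/100) = 0.111, against 0.12 stated. The difference is conservative and does not bear on this point.
- The follow-up phase has no stated size or precision to reproduce.

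**5. Reaching the trigger by chance.** For a normal change with mean μ and SD σ, P(change ≤ −0.5) = Φ((−0.5 − μ)/σ):

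| σ | μ = 0.01 | μ = 0.07 |
|---|---|---|
| 0.30 | Φ(−1.700) = 4.5% | Φ(−1.900) = 2.9% |
| 0.40 | Φ(−1.275) = 10.1% | Φ(−1.425) = 7.7% |
| 0.48 | Φ(−1.063) = 14.4% | Φ(−1.188) = 11.8% |

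At the planning SD this is about 8 to 10 per 100 completers. SAP section 1 records that enrolment stopped early, so the percentage is more useful than the count.

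**6. Rebound, illustration only.** The mean selected change is μ − σφ(z)/Φ(z), where z = (−0.5 − μ)/σ. At σ = 0.4 and μ = 0.04 it is −0.685, which is 0.725 below the mean. If a fraction r of the change variance is transient error at the Month 12 visit, the expected rebound with no change of treatment is r × 0.725: 0.07, 0.18 or 0.36 for r = 0.10, 0.25 or 0.50. The value of r is assumed; 0.50 is the maximum if errors are independent between visits. The formula also takes the reading that triggers entry to be the reading analysed, which is not so here.

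**The case against.** The phase is optional, depends on site interest and needs separate consent. Reversibility is neither a primary nor a secondary objective, and SAP 7 plans no formal testing. SAP section 1 reports the regulator's decision in terms of discontinuing treatment, so a real stop may be what was meant. All of this stands, and it limits the importance of the point. It does not settle the meaning, because the operative text still uses study drug and allows commercial topiramate.

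A reader might infer that children on and off topiramate cannot be told apart at all. The documents do not support that: the Month 13 call should show early status, and the gap is in later changes. Nor does any section classify a child still on topiramate as off it; the problem is ambiguity and pooling.

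On selection, a reader might take the rebound in step 6 as an estimate. It is not one. Entry uses local reads and analysis uses central reads, so local reading error that triggers entry need not carry into the analysed Month 12 value. Protocol 9.3 adds a central quality re-read after such a fall, the same machine throughout, and a goal of two clean scans per visit. These reduce the rebound but do not remove transient variation in the child.

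It is also tempting to rest reversibility on children who stopped versus those who continued, since both met the same trigger. That choice is not randomised, and the site has the local Month 12 result when it is made. If larger falls prompt stopping, the two groups will regress differently.

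**Conclusion.** The point holds as a limit on what the follow-up can show. Carried out as written, it can pool children still on topiramate with children off it, and routine records do not cover changes after Month 13. Any recovery would be diluted in proportion to the share continuing, which the documents do not give.

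Some rebound is also expected from selection alone. About 8% to 10% of children would meet the trigger by chance at SD 0.4, and about 3% to 14% over SD 0.3 to 0.48. This assumes a normal distribution, a single skeletal site and healthy 6- to 15-year-old values applied to children aged 2 to 15. The size of the rebound cannot be derived from the documents.

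The documents do not show that a conclusion of either kind will be drawn; SAP 7.4 promises only a summary and a listing. The primary comparison is untouched.

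**What to change.** 1. At the existing repeat-scan visit, record start and stop dates of topiramate from any source and of every other AED.
2. In SAP 7.4, report the change from Month 12 to the repeat scan, on central reads, for three groups: off topiramate throughout, on it throughout, and mixed. Add time since the last topiramate dose. Give the repeat scan its own label, since SAP Table 8 has no window for it and its Month 12 window is open-ended.
3. Label the results descriptive. State that neither rebound in the off-drug group alone nor the non-randomised difference between off and on establishes reversibility.
4. Keep a single scan date. State in protocol and SAP that stopping study drug does not imply stopping topiramate. A second clock running from the last topiramate dose could give one child two scan dates.
5. Reconcile the SAP 7.4 trigger (Month 6 or 12, no arm named, height-adjusted Z-score added) with Protocol 3.1, SAP 2.2 and the SAP schedule footnote (after one year, topiramate, and local scan in the protocol and footnote). SAP 2.5 and 7, which mention local reading at baseline only, need the same check.

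The cost is one medication entry, one table split and some wording. There are no extra scans and no treatment decision changes. The groups will be small, and the new record helps only children not yet rescanned unless dates can be recovered for the others.

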3.2. Study Design Rationale

A study population from 2 to 15 years of age is appropriate for this study because this is the approved pediatric age group for topiramate monotherapy. Levetiracetam is indicated as adjunctive therapy for POS in adults and children ≥ 1 month of age with epilepsy), PGTCs (adults and children ≥ 6 years of age with idiopathic generalized epilepsy), and myoclonic seizures (adults and children ≥ 12 years of age with JME). It has been studied as monotherapy in pediatric subjects down to neonates and has been demonstrated to be effective and safe in all treatment settings. Evaluation of this target age group will provide long-term systematic assessments of important safety issues, eg, chronic metabolic acidosis and effects on growth, bone mineralization, and nephrolithiasis. Subjects will be stratified by country and by age (2 to 5 years of age, 6 to 9 years of age, 10 to 12 years of age, and 13 to 15 years of age) in order to examine any differences in the safety profile between prepubescent children and postpubescent adolescents. A study duration of 1 year is appropriate in order to detect clinically important treatment-related effects on key safety parameters (growth retardation, bone mineralization, or kidney stone formation). See also Section 16.1, Study-Specific Design Considerations.

3.2.1. Blinding

The study is designed as an open-label study to enhance subject participation and completion and to simulate a naturalistic treatment setting. Given the technical challenges regarding blinding of study drug, along with the prolonged blinding required in young children and possible consequent impact on study conduct and results (eg, difficult regimens requiring too many tablets may result in poor compliance, protocol violations, or subjects prematurely dropping out of the study), a double-blind approach is not optimal. An open-label study is considered to be optimal given that the study population will include pediatric subjects down to 2 years of age and the study duration will be 1 year. An open-label design allows flexibility in dosing regimens.

To minimize any bias in measurement, after randomization 3 of the safety assessments will be obtained in a blinded fashion, including the DEXA scan, renal ultrasound, and height. These are the key assessments that are being evaluated on the basis of the biological effects associated with topiramate, and are necessary for achieving the primary objective.

3.2.2. Active Control

An active control will be used as opposed to a placebo control because of obvious ethical concerns of placebo treatment in a long-term monotherapy treatment setting for epilepsy, a chronic and potentially life-threatening disorder. Randomization will be used to minimize bias in the assignment of subjects to treatment groups, to increase the likelihood that known and unknown subject attributes (eg, demographic and baseline characteristics) are evenly balanced across treatment groups, and to enhance the validity of statistical comparisons across treatment groups.

Levetiracetam is an appropriate comparator because of its established efficacy for target seizure types, relatively low toxicity, and lack of significant known risk of kidney stones or possible deleterious effects on bone or growth. Levetiracetam is not approved as monotherapy for epilepsy; however, studies of children with epilepsy support its use in this indication. Notably, these monotherapy studies used the same titration and maintenance dosing as pivotal adjunctive studies; overall efficacy and safety outcomes were similar in both treatment settings.^{21,24,29,43} On this basis, the FDA-approved dosing recommendations for levetiracetam (titration schedule, dosing frequency) will be used in this study.

Study drug will be given as monotherapy only, since use of any concomitant AED may potentially confound results. However, subjects will not be discontinued from the study if 1 or more concomitant AEDs are added after initiating treatment with study drug. Data will be collected prior to the use of the concomitant AED(s) for the primary analysis. Data subsequently collected while on the concomitant AED(s) will be analyzed in a secondary analysis for each safety outcome of interest.

